### *2.3.1.2 Mycological Efficacy Parameters*

#### *2.3.1.2.1 Mycological Outcome*

Samples of ear discharge will be taken at V1, and in addition at visits V2, V3 and V4, when discharge is present. The otorrhea/debris sample will be taken prior to the debridement of the affected ear. A central laboratory will provide exudate sampling kits with standardized instructions for sample preparation (as defined in the Laboratory manual).

The otorrhea/debris sample will be sent to the Central Laboratory for processing. The central laboratory will be blinded to the treatment assignment of the patient from whom the sample was taken.

The central laboratory will use standardized microbiological laboratory procedures to identify fungal and bacterial species. If the culture does not show growth of any fungal pathogen from central laboratory or the local laboratory sent the wrong organism to central laboratory, the mycological result from local laboratory will be used.

Susceptibility testing will be performed on fungal isolates that are present at baseline and TOC for an individual subject according the Clinical and Laboratory Standard Institute methods for clotrimazole and comparator drugs to which the fungal isolates are susceptible.

For any patient with a culture positive for fungi at Visit 1, mycological outcome at Visit 2 will be classified as:

- Eradication if the culture does not show growth of any fungal pathogen;
- Presumed Eradication if there is no material to culture and the Overall Clinical Outcome is Clinical Cure;
- Persistence if any fungal pathogen cultured at Visit 1 is still present;
- Presumed Persistence: if there is no material to culture or sample was not taken or sample was not shipped to lab and the Overall Clinical Outcome is not Clinical Cure;
- Superinfection if a new fungal pathogen not present at Visit 1 is isolated while the initial pathogen is also present (presence of a nonpathogenic organism will not be considered Superinfection);
- Reinfection: if there is isolation of a new fungal pathogen different from the one present at Visit 1 and the initial pathogen is not present; or
- Indeterminate if none of the above definitions are met and the mycological outcome cannot be determined.

For any patient with a culture positive for fungi at Visit 1, mycological outcome at Visit 3 will be classified as:

- Eradication if the culture does not show growth of any fungal pathogen;

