For any patient with non fungal pathogen at Visit 1, mycological response at Visit 2 will be classified as:

- Presumed Eradication if the culture does not show growth of any fungal pathogen or if there is no material to culture and the Overall Clinical Outcome is Clinical Cure;
- Presumed Persistence if the Overall Clinical Outcome is Clinical Failure but no culture result is available;
- Superinfection if a pathogen not present at Visit 1 is now present; or
- Indeterminate if none of the above definitions are met and the mycological response cannot be determined.

For any patient with non fungal pathogen at Visit 1, mycological response at Visit 3 will be classified as:

- Presumed Eradication if the culture does not show growth of any fungal pathogen or if there is no material to culture and the Overall Clinical Outcome is Clinical Cure;
- Presumed Persistence if any fungal pathogen cultured at Visit 2 is still present or if the Overall Clinical Outcome is Clinical Failure but no culture result is available;
- Superinfection if a pathogen not present at Visit 1 and Visit 2 is now present;
- Indeterminate if none of the above definitions are met and the mycological response cannot be determined.

For any patient with non fungal pathogen at Visit 1, mycological response at Visit 4 will be classified as:

- Presumed Eradication if the culture does not show growth of any fungal pathogen or if there is no material to culture and the Overall Clinical Outcome is Clinical Cure;
- Presumed Persistence if any fungal pathogen cultured at Visit 2 and 3 is still present or if the Overall Clinical Outcome is Clinical Failure but no culture result is available
- Recurrence if a pathogen isolated at Visit 2, which was not present at Visit 3, reappears at Visit 4
- Superinfection if a pathogen not present at Visit 1, Visit 2 and Visit 3 is now present;
- Indeterminate if none of the above definitions are met and the mycological response cannot be determined.

The above rules will be used for microbiological outcome summaries for the patients in the clinical intent-to-treat (CITT) populations that have no pathogen at Visit 1, since mycological response cannot be calculated without any pathogen at Visit 1.

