### 3.3.3 Demographic and Baseline Characteristics

The following demographic and baseline characteristics will be summarized:

- Age (years) and age categories (<65 years, ≥65 years)
- Sex
- Childbearing potential
- Race
- Ethnicity
- Risk factors for otomycosis (exposure to excess moisture, trauma, use of hearing aids, topical otic antibacterial, quantitative or qualitative changes in earwax, other)
- Bilateral otomycosis (yes, no)
- Evaluable ear (left, right)
- Baseline pathogen (yes [fungal only, fungal and bacterial, bacterial only], no)
- Ear wick placement
- Baseline pathogen species

Demographic and baseline characteristics will be summarized with descriptive statistics or counts and percentages of subjects as appropriate by treatment and in total based on Safety, CITT, and MITT Population.

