#### *3.4.2.1 Mycological outcome*

The proportion of patients with a response of Eradication or Presumed Eradication at Visit 2, Visit 3 (EOT) and Visit 4 (TOC) will be compared between the Clotrimazole 1% otic solution and the Placebo treatment groups by using a chi-squared test, under a two-sided 5% significance level. The 95% confidence intervals together with the p-value based on the normal approximation to the binomial distribution will be presented for the between-treatment group differences. For each treatment group, the 95% confidence intervals using the Clopper-Pearson method will also be presented.

Mycological outcome will be summarized by treatment group and visit in terms of proportion in each category at each visit.

If a patient took rescue medication prior to Visit 3, the response will be considered a failure at Visit 3. Similarly, if a patient took rescue medication prior to Visit 4, the response will be considered a failure at Visit 4.

Responses will be summarized in terms of a 3-level response. Responses of Eradication or Presumed Eradication will be categorized as favorable. Responses of Persistence, Presumed Persistence, Superinfection, Reinfection, and Recurrence will be categorized as unfavorable. Indeterminate responses will be categorized as indeterminate. The proportion of patients with a favorable response at Visit 2, Visit 3 and Visit 4 will be compared between the Clotrimazole and Placebo treatment groups by using the same chi-squared test as the primary efficacy endpoint.

Mycological outcome will also be presented by pathogen on the MITT population (Candida spp, Aspergillus spp).

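### For patients with no fungus at Visit 1, the SAP's mycological rules let a bacterium-only follow-up culture be both favorable and unfavorable in the supportive CITT summaries

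*SAP*

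**What the plan says.** SAP 2.3.1.2.1 has two sets of rules. One is for patients whose Visit 1 culture grew a fungus, the other for patients with no fungal pathogen at Visit 1. A closing sentence assigns the second set to microbiological summaries in the CITT population.

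In the second set:
- The favorable category is "Presumed Eradication if the culture does not show growth of any fungal pathogen". An alternative clause covers patients with no material to culture, and a Clinical Cure condition follows.
- Superinfection at Visit 2 is "Superinfection if a pathogen not present at Visit 1 is now present; or". At Visit 4 it is "Superinfection if a pathogen not present at Visit 1, Visit 2 and Visit 3 is now present". Visit 3 has the same form.
- Recurrence exists only at Visit 4: "Recurrence if a pathogen isolated at Visit 2, which was not present at Visit 3, reappears at Visit 4".
- The Visit 4 rule "Presumed Persistence if any fungal pathogen cultured at Visit 2 and 3 is still present" is limited to fungi and names both earlier visits.
- Indeterminate applies when no other definition is met and the response cannot be determined.

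For patients with a fungus at Visit 1, the corresponding rule is "Superinfection if a new fungal pathogen not present at Visit 1 is isolated while the initial pathogen is also present".

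SAP 3.4.2.1 groups Presumed Eradication with the favorable responses and then says: "Responses of Persistence, Presumed Persistence, Superinfection, Reinfection, and Recurrence will be categorized as unfavorable". SAP 3.4.1 and 3.4.2 repeat the primary and secondary analyses on CITT as supportive work.

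**The concern.** The favorable rule asks about fungi only. Two of the unfavorable rules ask about any pathogen. The difference matters only if bacteria can be isolated and count as pathogens. In this trial the central laboratory identifies bacterial species, and bacterial cultures are scheduled at every visit (after Visit 1, when discharge or debris is present). The baseline table in SAP 3.3.3 uses the word to include bacteria: "Baseline pathogen (yes [fungal only, fungal and bacterial, bacterial only], no".

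A programmer coding the list as written would therefore find some patients in two categories on opposite sides of the favorable/unfavorable line, with nothing in the SAP to say which wins. A bacterial isolate is also not evidence about the mycological effect of an antifungal, so coding it as a mycological failure would be wrong in substance. The Protocol gives no fallback: its section 7.1.2.1 defines outcomes only for patients with a positive fungal culture at Visit 1.

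**Working it through.** **1. Visit 2, rules taken literally.** The Clinical Cure condition in Presumed Eradication can be read as qualifying only the no-material clause (reading A) or both clauses (reading B). For a patient with material cultured:

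| Visit 2 culture | TSSS | Reading A | Reading B |
|---|---|---|---|
| No fungus, no new bacterium | 0 | Presumed Eradication | Presumed Eradication |
| No fungus, no new bacterium | >0 | Presumed Eradication | Indeterminate |
| No fungus, new bacterium | 0 | **Presumed Eradication and Superinfection** | **Presumed Eradication and Superinfection** |
| No fungus, new bacterium | >0 | **Presumed Eradication and Superinfection** | Superinfection |
| Fungus | any | Superinfection | Superinfection |

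The overlap exists under both readings: at any TSSS under A, only at TSSS = 0 under B.

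**2. Visit 4, rules taken literally.** Allow four culture states at each of Visits 2, 3 and 4 (no material, negative, bacterium, fungus), with one bacterium and one fungus, both absent at Visit 1, and Clinical Cure at Visit 4. That gives 4 × 4 × 4 = 64 sequences.

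- *Bacterium at Visit 4 (16 sequences).* All meet Presumed Eradication. If the bacterium was absent at Visits 2 and 3 (3 × 3 = 9), Superinfection is also met. If it was present at Visit 2 and absent at Visit 3 (3), Recurrence is also met. So 9 + 3 = 12 of 64 are double-classified. In the other 4 the bacterium was already present at Visit 3, and only Presumed Eradication applies.
- *Fungus at Visit 4 (16 sequences).* Superinfection takes 9, Recurrence 3, and Presumed Persistence 1 (fungus at both Visits 2 and 3). The remaining 3 have the fungus at Visits 3 and 4 but not at Visit 2. They fail Presumed Persistence (not at Visit 2), Recurrence (not at Visit 2, and present at Visit 3) and Superinfection (present at Visit 3), so no specific category fits.

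These are counts of possible patterns, not of expected patients.

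**3. How many patients the rules can reach.** SAP 2.2.4 expects 21% with negative baseline mycology. Its own figure reproduces by arm: 100 / 0.79 = 126.6, rounded up to 127; 50 / 0.79 = 63.3, rounded up to 64; total 191. The group under these rules is then about 191 × 0.21 = 40.1, or 191 − 150 = 41 (27 clotrimazole, 14 placebo) by subtraction.

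This is an upper bound. The closing sentence of the section speaks of patients with no pathogen at Visit 1. If bacteria count as pathogens, that excludes patients with bacteria only at baseline.

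**4. Effect on the CITT favorable-response rate.** If a share *f* of the group has a bacterium-only culture that is double-classified at a visit, the choice of category moves the overall rate by 40*f* / 191. The documents give no value for *f*. As assumptions only:
- *f* = 5%: 2 patients, 2 / 191 = 1.0 point.
- *f* = 30%: 12 patients, 12 / 191 = 6.3 points.

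Equal shares nearly cancel between arms (27*f* / 127 = 0.213*f* against 14*f* / 64 = 0.219*f*). An assumed 30% on clotrimazole and 10% on placebo would move the difference by 0.3 × 27/127 − 0.1 × 14/64 = 6.4 − 2.2 = 4.2 points.

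**5. After the correction.** With both rules limited to fungi, all 16 sequences ending in a bacterium are Presumed Eradication only. With Visit 4 Presumed Persistence tied to Visit 3, the 16 fungal sequences split 4 Presumed Persistence, 3 Recurrence and 9 Superinfection. None is left over and none is counted twice.

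**The case against.** The best answer is that the SAP settles the matter elsewhere. Mycological cure is defined by the absence of fungal growth (2.3.1.2.1 and 3.4.1). No response is tied to a fungal pathogen, whether found in a fungal or a bacterial culture (2.1.1). Therapeutic failure needs a positive fungal culture or TSSS above 0 (2.3.1.3). The section is about mycology, the parallel list says fungal, and the closing sentence reasons that response cannot be calculated without a pathogen at Visit 1, where the word most naturally means a fungus. A sensible programmer would read it that way.

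Much of this stands, and it limits what can be claimed:
- A reader might infer that the CITT cure rates will be wrong by several points. The documents do not show that. The cure definitions point to fungal growth, and any such figure rests on assumed rates.
- A reader might infer that therapeutic cure shifts as much as mycological response. It cannot be affected unless TSSS = 0. Otorrhea is then absent, so the culture has to come from residual debris.
- A new bacterium does not trigger Recurrence. That needs one isolated at Visit 2, absent at Visit 3 and back at Visit 4. Protocol 8.2.4 names only a mycological culture at Visit 4, although both schedules list bacterial culture too.
- A reader might infer that the Visit 4 gap lets a culture-positive patient escape failure. It does not. Indeterminate outcomes count as failures (SAP 3.1.3), and a positive fungal culture is a therapeutic failure. Strictly, the patient may be unclassified rather than Indeterminate, since an outcome with fungus growing can be determined.

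The intended meaning does not remove the conflict itself. The category table, the 3-level summary and the favorable-response comparison in SAP 3.4.2.1 are built from the category labels, and the labels as written contradict the cure definition.

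**Conclusion.** The rules are wrong as written, in a minor way. For patients without a fungal pathogen at Visit 1, a follow-up culture with a new bacterium (or, for Visit 4 Recurrence, a returning one) and no fungus is both favorable and unfavorable. This holds at any TSSS or only at TSSS = 0, depending on how the Clinical Cure condition is read. It also conflicts with the SAP's own fungal-growth definitions of cure and failure.

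The reach is limited to the supportive CITT mycological category, 3-level and favorable-response summaries. CITT therapeutic cure is touched only possibly: at TSSS = 0, a patient labeled Superinfection for a bacterium meets neither the cure nor the failure definition in SAP 2.3.1.3. The primary analysis is untouched, because MITT requires a positive baseline culture for Aspergillus or Candida. About 40 of 191 patients is the ceiling on who is covered, and the actual effect is unknown.

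The Visit 4 gap is a labeling error in the 3-level table and moves no cure rate.

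**What to change.** In SAP 2.3.1.2.1, in the rules for patients with no fungal pathogen at Visit 1:
- Write *a fungal pathogen* in the Superinfection rules for Visits 2, 3 and 4 and in the Visit 4 Recurrence rule.
- In the Visit 4 Presumed Persistence rule, refer to a fungus cultured at Visit 3 instead of at Visits 2 and 3. A fungus seen at Visit 2, gone at Visit 3 and back at Visit 4 stays Recurrence.

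If the sponsor does want bacteria to count, the SAP has to state which category takes precedence.

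The cost is a few words and one derivation in the programming specification, before database lock. No new data are needed, and the one edit serves both CLEAR-1 and CLEAR-2, which share this SAP. A separate descriptive table of new bacterial isolates is optional. The change removes the overlap under either reading of the Clinical Cure condition but does not settle which reading is meant.

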#### *2.3.1.3 Therapeutic response*

The therapeutic response is a combined assessment of the Overall Clinical Outcome plus the Mycological Outcome. The following categories are defined:

1. Therapeutic cure: TSSS (pruritus + otalgia + ear fullness + otorrhea) = 0 and mycological outcome eradication or presumed eradication.
2. Therapeutic failure:
  - Positive fungal culture, OR
  - TSSS > 0 regardless of mycological outcome.

#### *2.3.1.4 Primary Efficacy Endpoint*

Based on the definitions in Section 2.3.1.1.5, 2.3.1.2 and 2.3.1.3, the primary efficacy endpoint will be the proportion of patients with Therapeutic cure at Test of Cure (Visit 4) in the MITT population.

#### *2.3.1.5 Secondary Efficacy Endpoints*

Based on the definitions in Sections 2.3.1.1, 2.3.1.2 and 2.3.1.3, the secondary efficacy endpoints will be:

- Overall clinical cure at Visits 2, 3 and 4.
- Mycological cure at Visits 2, 3 and 4.
- Therapeutic cure at Visit 2 and 3.
- Changes in TSSS at Visits 2, 3 and 4.
- Changes in individual signs and symptoms at Visits 2, 3 and 4.

In the case of bilateral otomycosis the non-selected ear will also be treated and assessed for its clinical evolution.

### 2.3.2 Safety Parameters

Safety will be assessed by adverse events (AEs) and physical examination. In addition, a urine pregnancy test for females of childbearing potential will be performed at Visit 1.

#### 2.3.2.1 Adverse Events

Adverse events will be recorded throughout the study and at early termination, and will be coded using the Medical Dictionary for Regulatory Activities (MedDRA).

An AE is any untoward medical event that occurs in a patient or subject who has received an investigational product, whether or not considered drug related. An AE can therefore be any unfavorable and unintended sign (including abnormal laboratory finding), symptom, or disease temporally associated with the use of an investigational product, whether or not related to the study product.

An illness present at entry to the study is considered a pre-existing condition and will not be considered an AE. However, if a pre-existing condition worsens during the study, this may be considered an AE. Pre-existing conditions will be documented in the Electronic Data Capture (EDC). If pre-existing signs and signs/symptoms of otomycosis (pruritus, otalgia, ear fullness and otorrhea) worsen during the study, this will be considered a treatment failure instead of an AE.

#### 2.3.2.2 Physical Examination

Physical examination will be performed at V1. A directed examination of the ears (external inspection and examination (with or without microscope) of the external auditory canal), head, nose and oropharynx will be performed.

#### 2.3.2.3 Vital Signs

Vital signs (temperature, blood pressure, and pulse) will be assessed at all visits.

#### 2.3.2.4 Pregnancy Test

A urine pregnancy test will be performed at Visit 1 for female patients of childbearing potential (females who have had menarche and are not premenstrual, not postmenopausal or not surgically sterile).

## 3 STATISTICAL METHODOLOGY

### 3.1 General Considerations

#### 3.1.1 Definition of Baseline

For microbiological data, baseline pathogen(s) are determined from the samples collected prior to the first dose of study drug.

For all efficacy and safety endpoints, baseline is defined as the last measurement or assessment prior to the first dose of study drug.

#### 3.1.2 Summary Statistics

Categorical data will generally be summarized with counts and percentages of subjects. The denominator used for the percentage calculation will be clearly defined. Continuous data will generally be summarized with descriptive statistics including n (number of non-missing values), mean, median, standard deviation, minimum, and maximum.

### 3.1.3 Handling of Dropouts and Missing Data

Patients with missing efficacy data or indeterminate outcomes will be considered as treatment failures for efficacy analyses.

For the primary and secondary endpoints, patients who discontinue for lack of efficacy or rescue medication will be considered as treatment failures.

In cases of missing or incomplete dates (e.g. AE and concomitant medications), the missing component(s) will be assumed as the most conservative value possible. For example, AEs with missing start dates, but with stop dates either overlapping into the treatment period or missing, will be counted as treatment-emergent, taking the worst-case approach. When partial dates are present in the data, both a partial start date and/or a partial stop date will be evaluated to determine whether it can be conclusively established that the AE started prior to the start of study drug or ended prior to the start of study drug. If the above cannot be conclusively established based on the partial and/or present dates, then the AE will be considered as treatment-emergent. Actual data values as they appear in the original electronic Case report form (eCRF) will be presented in the data listings.

Missing values for other variables will not be imputed and only observed values will be used in data analyses and summaries.

## 3.2 Analysis Populations

There will be 4 populations defined for this study: Safety, CITT, MITT, and Mycological per-protocol (MPP).

### 3.2.1 Safety Population

The Safety population will include all patients who received any study medication.

### 3.2.2 Clinical intent-to-treat (CITT)

The CITT population will include all patients who were randomized.

### 3.2.3 Mycological intent-to-treat (MITT)

The MITT population will include all CITT patients who had a positive baseline fungal culture for *Aspergillus spp* and/or *Candida spp*. The primary populations for efficacy analyses will be the MITT population.

### 3.2.4 Mycological per-protocol (MPP)

The MPP population will include all randomized patient who had positive baseline culture for *Aspergillus spp* and/or *Candida spp* and who:

- Satisfied all inclusion and exclusion criteria;
- Did not receive any prohibited concomitant medications (except if it is considered rescue medication);
- Did not have any other major protocol violations;
- Completed Visit 2;
- Completed Visit 3 and Visit 4 (unless the subject was deemed a clinical failure at an earlier visit than Visit 4);
- Completed Visit 4 within the designated visit window;

- Had compliance rates between 80% and 100% as defined in Section 3.3.7 (patients who are deemed Clinical Failures are to be included if they had compliance rates between 80% and 100% during the first 3 days of study treatment);
- Had mycological results (when subject has material to culture) from Visit 1, Visit 2, Visit 3 and/or Visit 4 unless the subject was deemed a clinical failure at an earlier visit than Visit 4.

For the CITT and MITT populations, the treatment group of a patient will be determined by the treatment group to which the patient was randomized.

For the Safety and MPP populations, the treatment group of a patient will be determined by the treatment the patient received, not necessarily the group to which he or she was randomized. The Safety population will be used for all safety analyses.

